**Table 1 List of Laboratory Parameters**

Clinical Chemistry	Hematology
Blood urea nitrogen	White blood cell (WBC) count
Potassium	Red blood cell (RBC) count
Sodium	Hemoglobin
Aspartate Aminotransferase	Hematocrit
Total and Direct Bilirubin	Mean corpuscular volume
Creatinine	Mean corpuscular hemoglobin
Glucose non-fasting	Mean corpuscular hemoglobin concentration
Chloride	Red cell distribution width
Bicarbonate/CO2	Platelet
Serum Glutamic-Oxaloacetic Transaminase	Mean platelet volume
Alanine Aminotransferase	Methemoglobin
Serum Glutamic-Pyruvic Transaminase	
Alkaline phosphatase	
Lactate dehydrogenase	
Coagulation	
	Prothrombin Time
	International Normalized Ratio
	Activated Partial Thromboplastin Time

To assess Hy's Law, the number and percentage of patients with potentially clinically significant post-baseline elevations in hepatic parameters shown in Table 2 below will be summarized by treatment.

A listing of the patients with potentially clinically significant post-baseline hepatic elevations will be provided. The listing will contain all a subject's values for parameters meeting the criteria.

**Table 2. Potentially Clinically Significant Elevations in Hepatic Parameters**

ALT-absolute	ALT $\geq$ 8xULN
ALT Increase	ALT $\geq$ 5xULN but $<$ 8xULN persists for $\geq$ 2 weeks ALT $\geq$ 3xULN but $<$ 5xULN persists for $\geq$ 4 weeks
Bilirubin	ALT $\geq$ 3xULN and bilirubin $\geq$ 2xULN ( $>$ 35% direct bilirubin)
INR^2	ALT $\geq$ 3xULN and international normalized ratio (INR) $>$ 1.5, if INR measured

\* ALT = Alanine aminotransferase;

1. Serum bilirubin fractionation should be performed if testing is available. If serum bilirubin fractionation is not immediately available, discontinue study intervention if ALT  $\geq$ 3xULN **and** bilirubin  $\geq$ 2xULN. Additionally, if serum bilirubin fractionation testing is unavailable, **record the absence/presence of detectable urinary bilirubin on dipstick** which is indicative of direct bilirubin elevations suggesting liver injury.
2. All events of ALT  $\geq$ 3xULN **and** bilirubin  $\geq$ 2xULN ( $>$ 35% direct bilirubin) or ALT  $\geq$ 3xULN **and** INR  $>$ 1.5 may indicate severe liver injury (**possible 'Hy's Law'**) **and must be reported as an SAE (excluding studies of hepatic impairment or cirrhosis)**. The INR stated threshold value will not apply to participants receiving anticoagulants.

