### 3 INVESTIGATIONAL PLAN

### 3.1 Overall Study Design and Plan

This is an open-label, randomized, multicenter, parallel group, concurrent, controlled study using a sequential adaptive design to evaluate the efficacy and safety of RESP301 added to standard of care (SOC) in hospitalized patients with COVID-19 (WHO ordinal scale grade 3 & 4).

Central stratified randomization of 300 subjects to assign participants into one of the study treatment arms will occur as follows, RESP301+SOC or SOC (control), with a randomization ratio of 2:1 using an interactive voice response system (IVRS)/interactive web response system (IWRS). Participants will be stratified by country and presence of risk factors for severe outcomes of COVID-19, based on comorbidities and age as follows:

1. Age  $>65$  years
2. Ongoing or currently treated diabetes mellitus
3. Ongoing or currently treated hypertension
4. Ongoing or currently treated cardiovascular disease
5. Ongoing or currently treated chronic lung disease
6. Cancer history of less than 3 years, basal cell skin carcinoma excluded
7. Ongoing or currently treated chronic kidney disease

Participants will be stratified as no risk factor (none of the above criteria), one risk factor (one single of the above) or high-risk factor (2 or more of the above).

There are 3 phases in the overall study design: Screening Period, Intervention Period, Follow-up Period. Figure 1 displays the study schematic.

**Screening Period**– Patients will be screened up to 2 days prior to treatment administration. Upon signing informed consent, the patient enters the screening phase and is assessed for the inclusion/exclusion criteria. If all eligibility criteria are met, the patient moves into the intervention period.

[figure not shown]
**Intervention Period** – The intervention period starts on Treatment Initiation (Day 1). Patients will receive treatment three times a day up to Day 10. Patients may end treatment earlier than Day 10 if their symptoms subside following the criteria outline in the protocol section 4.1.

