#### Follow-up Period

- For efficacy - patients will be followed up on Day 14 and Day 28. If patient is no longer hospitalized, follow-up will occur by phone-call.
- For safety - patients will be follow-up 28 days after the first treatment dose is administered. If patient is no longer hospitalized, follow-up will occur by phone-call.

Two interim analyses are planned to assess futility. The first IDMC interim analysis will take place after the first 60 participants have completed Day 10 of the study to evaluate whether the study will be stopped for futility based on change from baseline in room air SpO2. The second interim analysis will take place after 150 participants have completed Day 14 post-randomization based on event rate for the primary endpoint. The purpose of the second interim analysis will be futility as well as a potential sample size re-estimation in case the actual results differ from the original assumptions.

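### Table 2 counts an isolated ALT rise of 3 to <8xULN only if it persists for 2 or 4 weeks, a condition that follow-up can hardly show at 4 weeks and that depends on length of stay at 2 weeks

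*SAP*

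**What the plan says.** Section 4.10.3 of the current SAP (version 2.0) introduces Table 2 as the tool for assessing Hy's Law and states that "the number and percentage of patients with potentially clinically significant post-baseline elevations in hepatic parameters shown in Table 2 below will be summarized by treatment". Those who meet the criteria are also to be listed.

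Table 2 has four rows:

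- ALT ≥8xULN, with no duration condition.
- An ALT-increase row with two criteria: "ALT $\geq$ 5xULN but $<$ 8xULN persists for $\geq$ 2 weeks" and "ALT $\geq$ 3xULN but $<$ 5xULN persists for $\geq$ 4 weeks".
- ALT ≥3xULN with bilirubin ≥2xULN, with no duration condition.
- ALT ≥3xULN with INR >1.5, with no duration condition.

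On follow-up, Section 3.1 says for safety that "patients will be follow-up 28 days after the first treatment dose is administered. If patient is no longer hospitalized, follow-up will occur by phone-call". The notes to Figure 1 allow discharge before Day 10. Section 4.2 defines a duration as stop date minus start date plus one.

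The rest of Section 4.10.3 provides by-visit summaries of each laboratory parameter, CTCAE v5.0 grading of values, and a by-patient listing with abnormal values flagged and reference ranges shown.

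**The concern.** Persistence can be shown only by blood samples. The two persistence criteria ask for 14 and 28 days of raised ALT, counted from a post-baseline value, in a study whose safety follow-up stops at 28 days and becomes a telephone call after discharge. A telephone call gives no ALT value. So a patient with a clear but short isolated ALT rise between 3x and 8xULN enters no row of the table and is not on the hepatic listing.

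Two consequences follow. First, a zero or near-zero ALT-increase row would read as reassurance, although the rule had little chance of showing anything else. Second, the chance of meeting the 2-week criterion grows with time in hospital. Time to hospital discharge is an additional secondary endpoint in Section 3.3.1. If stay differs by arm, the chance of being counted differs too, and the comparison between arms is no longer one of liver safety alone.

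**Working it through.** The SAP states no figure on this point, so there is nothing to reproduce. The check is date arithmetic.

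**Inputs**
- Required persistence: 14 and 28 days (Table 2).
- Only post-baseline elevations count (text introducing Table 2).
- Duration = stop − start + 1 (Section 4.2).
- End of safety follow-up: 28 days after first dose. This is Day 28, or Day 29 if counted as Day 1 + 28 (Section 3.1).
- Assumption: the first post-baseline sample is on Day 2. The SAP does not give the sampling days. A raised post-dose sample on Day 1 is shown as the alternative.

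**Day on which a confirming raised sample is needed, first raised value on Day 2**
- 2-week criterion: 2 + 14 − 1 = Day 15.
- 4-week criterion: 2 + 28 − 1 = Day 29.
- If persistence were read as a plain difference without the +1: 2 + 14 = Day 16 and 2 + 28 = Day 30.

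**Longest span that can be observed**, by day of last blood sample (plain difference in brackets)

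| Last sample | From Day 2 | From a post-dose Day 1 sample | 2-week criterion | 4-week criterion |
|---|---|---|---|---|
| Day 10 | 9 (8) | 10 (9) | cannot be met | cannot be met |
| Day 14 | 13 (12) | 14 (13) | only from Day 1, with the +1 | cannot be met |
| Day 28 | 27 (26) | 28 (27) | can be met | only from Day 1, with the +1 |
| Day 29 | 28 (27) | 29 (28) | can be met | from Day 2 with the +1; without it, only from Day 1 |

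**Latest day on which the rise can first be seen and still qualify** (last sample − required days + 1)
- 2-week criterion: 28 − 14 + 1 = Day 15, or 29 − 14 + 1 = Day 16.
- 4-week criterion: 28 − 28 + 1 = Day 1, or 29 − 28 + 1 = Day 2.

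So the 4-week criterion needs ALT in range from the first day or two and a blood sample at the very end of follow-up. The 2-week criterion fits inside follow-up, but only for a patient with a blood sample about two weeks after the first raised value.

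**Illustration.** A patient has ALT 7.9xULN on Days 3 to 10, then no further sample, with normal bilirubin and INR. The observed duration is 10 − 3 + 1 = 8 days, below 14, and the value is below 8xULN. This patient is in no Table 2 row.

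**Other tables in Section 4.10.3.** The by-visit summaries describe the distribution of values, in SI units and against local normal ranges. They use the first non-missing assessment at each visit, so a peak on a repeat sample can drop out. Values are graded, but the section specifies no table of worst grade or grade shift. SAP version 1.0 did specify a summary of the maximum grade shift in its Section 4.10.3. The current text has none.

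**The case against.** The strongest case on the other side has four parts.

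- **Table 2 does what it is introduced for.** The Hy's Law rows (ALT with bilirubin, ALT with INR) and the ≥8xULN row carry no duration condition. This stands, and it limits the size of the problem.
- **Isolated rises are not lost.** They feed the by-visit summaries and are flagged in the laboratory listing. Section 4.2 also allows shift tables for categorical data where appropriate. This stands in part: a listing gives no count by arm, a by-visit distribution does not say how many patients reached a multiple of ULN, and the general wording on shift tables does not commit the laboratory section to one.
- **The 2-week criterion can be met.** A reader might infer that neither criterion can ever be satisfied, or that rises of 3 to <8xULN will be reported as absent whatever the drug does. The documents do not support that. Fourteen days fit inside 28, telephone contact applies only after discharge, the SAP gives no discharge rate, and the sampling schedule is left to the protocol. The 2-week criterion is restricted, not ruled out, and even the 4-week one can be met at the edge.
- **Dosing length is not the limit.** A reader might also argue from "Patients will receive treatment three times a day up to Day 10" that a 2-week elevation is impossible. An ALT rise can outlast dosing. What limits observed persistence is the last blood sample.

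**Conclusion.** The point holds in a limited form. The 4-week criterion is empty or nearly so by construction. The 2-week criterion is open only to patients still in hospital or re-sampled about two weeks after the first raised value, so being counted depends on length of stay. No table in the current Section 4.10.3 counts patients by peak ALT or worst grade to make up for this.

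The size is modest: a gap in safety reporting for isolated ALT rises of 3 to <8xULN. It does not affect the Hy's Law rows, the ≥8xULN row or any efficacy analysis. How many patients go uncounted cannot be worked out from the SAP.

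The conclusion rests on two assumptions: that the first post-baseline sample is on about Day 2, and that discharged patients are not routinely bled again. If the protocol schedules blood samples after discharge, the 2-week restriction eases. The 4-week criterion stays at the edge of follow-up in any case.

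**What to change.** In Section 4.10.3:

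1. Keep the existing Table 2 rows.
2. Add to the tabulation the number and percentage of patients in each arm whose maximum post-baseline ALT is ≥3x, ≥5x and ≥8xULN, regardless of duration and using all scheduled and unscheduled samples. Do the same for AST, which is already in Table 1.
3. Extend the hepatic listing to every patient with post-baseline ALT ≥3xULN.
4. State how persistence is derived: which samples start and end the period, whether the plus-one rule applies, and how a missing later sample or a value that moves between bands is treated.

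This changes reporting only and sets no clinical rule. How the persistence criteria fit the treatment and follow-up period must be reconciled with the protocol.

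The cost is SAP wording and a simple derivation from data already collected, with no new samples. The downside is small: more patients will appear in the table, some because of COVID-19 itself, and the concurrent control arm puts those in context.

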#### 4.10.4 Vital Signs, Physical Findings and Other Observations Related to Safety

Summaries for each vital sign parameter will be presented by treatment arm and visit. Observed and change from baseline values in vital sign results will be analyzed using descriptive statistics. Change from baseline will only apply to post-baseline assessments.

Shifts in ECG results, from baseline to each post-baseline visit (where available) will be summarized by treatment arm. The maximum shift (across all visits) in ECG results from baseline will also be summarized by treatment arm.

By-patient listings of vital sign data, ECG results, and physical examination results will be provided by treatment arm.

#### 4.10.5 Independent Data Monitoring Committee [IDMC]

An IDMC will be responsible for closely reviewing the safety and efficacy data from the interim analyses and for providing their recommendations on continuation of the study. The IDMC will

meet to review after 10 and 20 participants have completed as well as at the time of the two interim analyses (i.e., after 60 and 150 participants have completed; see [Section 4.9.1.5](#)).

[figure not shown]
The IDMC Charter will provide additional details about the IDMC activities. Table 3 outlines the IDMC meetings.

**Table 3: Scheduled IDMC Meetings**

Meeting	Timing	Review Type
1 st Data Review Meeting	After 10 patients	Safety
2 nd Data Review Meeting	After 20 patients	Safety
1 st Interim Analysis Meeting	After 60 patients have completed Day 10	Safety/ Futility/ Change in SpO 2
2 nd Interim Analysis Meeting	After 150 patients have completed Day 14	Safety/ Futility/ Superiority/ Sample Size Reassessment

#### 4.11 Determination of Sample Size

CCI

CCI  
CCI  
CCI

CONFIDENTIAL

Project Document Version No. 2.0  
Project Document Effective Date: Date of last signature  
Page 29 of 31

A horizontal bar chart showing the percentage of patients with a history of CCI across different age groups. The y-axis represents age groups: 18-29, 30-39, 40-49, 50-59, 60-69, 70-79, and 80+ years. The x-axis represents the percentage of patients, ranging from 0% to 100%. The bars are black, except for the first one which has a red 'CCI' label. The data shows that the percentage of patients with a history of CCI increases with age, with the highest percentage in the 80+ year group.

Age Group	Percentage of Patients with CCI
18-29	~10%
30-39	~15%
40-49	~25%
50-59	~35%
60-69	~45%
70-79	~55%
80+ years	~65%

#### 4.12 Changes in the Conduct of the Study or Planned Analysis

See Statistical Analysis Plan Addendum.

## 6 APPENDIX A

Table with examples for the adaptive sample size procedure described in [Section 4.11](#) using Cui/Hung/Wang (CHW) approach using a weighted test for the final analysis

2 nd IA results with n=150 patients (50 for SOC, 100 for RESP301+SOC)	CP under observed trend for planned 300	Total sample size required for CP 80% under observed trend	CP under observed trend if total sample size capped by 600
15 (30%)	5 (5%)	p < 0.0005 → early stop for superior efficacy	
15 (30%)	10 (10%)	99%	Not applicable
15 (30%)	15 (15%)	90%	Not applicable
15 (30%)	18 (18%)	66%	393
			Not applicable

# PAREXEL International

30 Respiratory Limited

RESP301

Statistical Analysis Plan

15 (30%)	19 (19%)	55%	483	Not applicable	
15 (30%)	21 (21%)	34%	[798]	[67%]	
15 (30%)	26 (26%)	3.99%	Early stop for futility		
12 (24%)	10 (10%)	92%	Not applicable	Not applicable	
12 (24%)	12 (12%)	77%	321	Not applicable	
12 (24%)	14 (14%)	54%	498	Not applicable	
12 (24%)	15 (15%)	42%	[646]	[77%]	
12 (24%)	18 (18%)	14%	[1800]	[31%]	
12 (24%)	20 (20%)	2.6%	Early stop for futility		
10 (20%)	8 (8%)	85%	Not applicable	Not applicable	
10 (20%)	10 (10%)	64%	412	Not applicable	
10 (20%)	11 (11%)	50.4%	534	Not applicable	
10 (20%)	13 (13%)	26%	[1014]	[55%]	
10 (20%)	15 (15%)	10%	[2460]	[23%]	
10 (20%)	18 (18%)	1.4%	Early stop for futility		

Signature Page for **CCI**

Reason for signing: Approved	PPD	21-Jan-2022 12:01:56 GMT+0000
Reason for signing: Approved	PPD	21-Jan-2022 12:09:12 GMT+0000
Reason for signing: Approved	PPD	-2022 13:49:21 GMT+0000
Reason for signing: Approved	PPD	Jan-2022 15:12:08 GMT+0000
Reason for signing: Approved	PPD	21-Jan-2022 15:37:06 GMT+0000

Signature Page for **CCI**

**REVISION HISTORY**

Version No.	Effective Date	Summary of Change(s)
1.0	16JUL2020	New document

**LIST OF ABBREVIATIONS**

Abbreviation / Acronym	Definition / Expansion
ADaM	Analysis Data Model
ADI	Actual Dose Intensity
AE	Adverse event
ANCOVA	Analysis of Covariance
BMI	Body Mass Index
BP	Blood pressure
CHW	Cui/Hung/Wang
CI	Confidence interval
CMH	Cochran Mantel Hensel
COVID	Coronavirus
CP	Conditional Power
CTCAE	Common Terminology Criteria for Adverse Events
DBP	Diastolic blood pressure
DoD	Date of Discharge
DRE	Disease Related Events
ECG	Electrocardiogram
FiO2	Fraction of Inspired Oxygen
IDI	Intended Dose Intensity
IDMC	Independent Data Monitoring Committee
ITT	Intent-to-Treat
LOCF	Last Observation Carried Forward
MedDRA	Medical Dictionary for Regulatory Activities
MMRP	Mixed Model Repeated Measures
NCI	National Cancer Institute
NEWS	National Early Warning Score
PP	Per Protocol Population
PT	Preferred Term
RBC	Red Blood Cells
RDI	Relative Dose Intensity

# PAREXEL International

30 Respiratory Limited  
RESP301

Statistical Analysis Plan

Abbreviation / Acronym	Definition / Expansion
SAP	Statistical Analysis Plan
SAE	Serious adverse event
SBP	Systolic blood pressure
SD	Standard Deviation
SOC	System Organ Class
SP	Safety Population
TID	Three Times a Day
WBC	White Blood Cells
WHO	World Health Organization

## 1 INTRODUCTION

Coronavirus disease 2019 (COVID-19) is a respiratory illness caused by a novel coronavirus (SARS-CoV-2). COVID-19 was first described in Wuhan, China, in December 2019 and is now a global pandemic (**Error! Reference source not found.**). Most of those affected have milder illness (80%), 15% will be severely ill (require oxygen) and 5% will require intensive care unit care (**Error! Reference source not found.**). Of those who are critically ill, most require early intubation and mechanical ventilation.

A critical early component of innate host defense in the airway is the ability of respiratory epithelial cells to produce high levels of NO (**Error! Reference source not found.**). NO functions as a signaling molecule in initiation of the inflammatory response to viruses, and also has direct antiviral effects (**Error! Reference source not found.**).

RESP301 is a NO-generating liquid designed to release NO in situ in the upper airways and deep in the alveolar spaces. RESP301 is delivered via a handheld nebulizer and has specific advantages over inhaled NO gas in treating patients with COVID-19 during the current pandemic.

This is an open-label, randomized, multicenter, parallel group, concurrent, controlled study using a sequential adaptive design. Participants will be consented and randomized 2:1 to the Investigational arm or the Control arm. Participants randomized to the Investigational arm will receive inhaled RESP301 (6 mL) administered using a nebulizer 3 times a day (TID) for up to 10 days in addition to the standard of care (SOC) while participants in the Control arm will receive SOC alone.

The analyses described in this SAP are based upon the following study documents:

- Study Protocol, Version 3.0 (June 10, 2020 )
- electronic Case Report Form (eCRF), Version 3.0 (June 24, 2020)
- RESP301 DMC Charter

## 2 STUDY OBJECTIVES

### 2.1 Primary Objective

- To evaluate efficacy of RESP301 in preventing progression of hospitalized COVID-19 participants at level 4 in the modified World Health Organization (WHO) ordinal scale into levels >4

### 2.2 Secondary Objectives

- To assess the effect of RESP301 as measured by room air SpO2
- To assess the effect of RESP301 as measured by the National Early Warning Score (NEWS) 2 symptom score

- To assess the treatment response on clinical status

### Additional Secondary Objectives

- To assess the overall safety profile of RESP301 in COVID-19 participants
- To assess the ability of participants to tolerate nebulization

### 2.3 Exploratory Objective

- CCI

## 3 INVESTIGATIONAL PLAN

### 3.1 Overall Study Design and Plan

This is an open-label, randomized, multicenter, parallel group, concurrent, controlled study using a sequential adaptive design to evaluate the efficacy and safety of RESP301 added to standard of care (SOC) in hospitalized patients with COVID-19 requiring supplemental oxygen.

Central stratified randomization of 300 subjects to assign participants into one of the study treatment arms will occur as follows, RESP301+SOC or SOC (control), with a randomization ratio of 2:1. Participants will be stratified by country and presence of risk factors for severe outcomes of COVID-19, based on comorbidities and age as follows:

1. Age >65 years
2. Ongoing or currently treated diabetes mellitus
3. Ongoing or currently treated hypertension
4. Ongoing or currently treated cardiovascular disease
5. Ongoing or currently treated chronic lung disease
6. Cancer history of less than 3 years, basal cell skin carcinoma excluded
7. Ongoing or currently treated chronic kidney disease

Participants will be stratified as no risk factor (none of the above criteria), one risk factor (one single of the above) or high-risk factor (2 or more of the above).

There are 3 phases in the overall study design: Screening Period, Intervention Period, Follow-up Period. Figure 1 displays the study schematic.

**Screening Period**— Patients will be screened up to 2 days prior to treatment administration. Upon signing informed consent, the patient enters the screening phase and is assessed for the inclusion/exclusion criteria. If all eligibility criteria are met, the patient moves into the intervention period.

[figure not shown]
**Intervention Period**— The intervention period starts on Treatment Initiation (Day 1). Patients will receive treatment three times a day up to Day 10. Patients may end treatment earlier than Day 10 if their symptoms subside following the criteria outline in the protocol section 4.1.

#### Follow-up Period

- For efficacy - patients will be followed up on Day 14 and Day 28. If patient is no longer hospitalized, follow-up will occur by phone-call.
- For safety - patients will be follow-up 28 days after the first treatment dose is administered. If patient is no longer hospitalized, follow-up will occur by phone-call.

Two interim analyses are planned to assess futility. The first IDMC interim analysis will take place after the first 60 participants have completed Day 10 of the study to evaluate whether the study will be stopped for futility based on change from baseline in room air SpO2. The second interim analysis will take place after 150 participants have completed Day 14 post-randomization based on event rate for the primary endpoint. The purpose of the second interim analysis will be futility as well as a potential sample size re-estimation in case the actual results differ from the original assumptions.

